$n = f(\alpha_s \ \beta) \ \times \ 2 \ \times \ \sigma^2 \ / \ d^2$		How to cite this service	
where σ is the standard deviation, and		Sealed Envelope Ltd. 2012. Power calculator for continuous	
$f(\alpha, \beta) = [\Phi^{-1}(\alpha) + \Phi^{-1}(\beta)]^2$		outcome non-inferiority trial. [Online] Available from: https://www.sealedenvelope.com/power/continuous-noninferior/	
• ¹ is the cumulative distribution function of deviate.	a standardised normal	[Accessed Thu Jan 19 2023].	

The power calculation suggests 417 patients in each group, the expected drop-out rate of patients is 20% (results from the SR pilot study, Ferretti et al 2024), resulting in 500 patients per group.

7. Randomization and Blinding

Randomization Method

At screening, the order of diagnostic tests will be randomized. The "randomization system" (RS) will assign an unique identification number to the patient known as the patient number. This number will be associated with the patient throughout the study. Each patient signing an informed consent form (ICF) must be entered into the RS regardless of eligibility to obtain a patient number. This 8-digit number will consist of a 3-digit country specific code, followed by a 2-digit site identification and a 3-digit number assigned sequentially within each site to each patient, starting at 001.

At the randomization visit, all eligible patients will be randomly assigned in a 1:1 ratio to follow the routine clinical management or to be part of the SR clinical pathway. Centres using polysomnography as routine sleep evaluation procedure are asked to use this method in all of the study patients at this centre, and vice versa for those centers using cardiorespiratory polygraphy as the routine method. By this procedure, the study aims to recruit at least 40% of patients in the traditional clinical routine to be assessed by PSG. No formal stratification for anthropometric factors like age, BMI, gender or comorbidities will be performed.

Patients will be assigned a randomization number through the RS. Once a randomization number is allocated to one patient, it may not be assigned to another patient even if the former discontinued the study. The randomisation list is exemplified in appendix B.

Blinding

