8.4. Primary Analysis

Primary outcome: Staff time– comparison between standard care and the Sleep Revolution model in patients with suspected obstructive sleep apnea (OSA).

• Primary Outcome

The primary outcome is staff time, spent for the sleep apnea diagnostic pathway (V1a to V1 c) measured in minutes, required per patient, for the randomized study procedure (SC or SR care).

• Study Design

This is a parallel-group design comparing two patient groups (Group A and Group B). Patients are nested within centers, and the analysis will account for potential clustering by center. This is a non-inferiority comparison in staff time.

• Analysis Population

The primary analysis will be conducted on the intention-to-treat (ITT) population, including all randomized patients according to their assigned group.

• Descriptive Statistics

Descriptive statistics will be presented for staff time by group, including:

- Mean (standard deviation), Median (interquartile range), and Minimum/Maximum

• Primary Analysis

To compare staff time between the two groups while adjusting for center effects, a linear mixedeffects model (LMM) will be used:

- Fixed effect: Group (Group A vs. Group B)
- Random effect: Center (to account for clustering)
- Model specification:

StaffTime_{ij} = $\beta_0 + \beta_1 * Group_{ij} + u_j + \varepsilon_{ij}$

where:

- StaffTime_{ij} is the staff time for patient i in center j
- β_0 is the intercept
- β_1 is the fixed effect of group
- u_j ~ N(0, σ_u^2) is the random effect for center
- $\varepsilon_{ij} \sim N(0, \sigma^2)$ is the residual error

Adjustment for potential confounders would be considered if groups are unbalanced for some covariate due to random.

• Estimates and Inference

The estimated mean difference in staff time between groups will be reported with 95% confidence intervals and p-values.

Model assumptions (normality of residuals, homoscedasticity) will be checked using diagnostic plots.

Sensitivity Analyses

A per-protocol analysis will be conducted to assess robustness.

If the distribution of staff time is highly skewed, a log-transformation or non-parametric methods may be considered.

Two additional sensitivity analyses will be performed based on patient characteristics like A) sex and B) by the median of the age (total patient population).

Further sensitivity analysis will be performed regarding subgroups of centers and patient characteristics for sleep test methodology in the standard care arm:

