8.10. Imputation of missing data

In the event of missing data, standard imputation procedures will be employed to ensure the robustness of the statistical analysis. The following steps will be taken to handle missing data: 1. Identification of Missing Data: The dataset will be examined to identify any missing values in the variables of interest.

2. Assessment of Missing Data Mechanism: The mechanism of missing data (Missing Completely at Random, Missing at Random, or Missing Not at Random) will be assessed to determine the appropriate imputation method.

3. Imputation Methods:

- Mean/Median Imputation: For continuous variables, missing values may be imputed using the mean or median of the available data.

- Regression Imputation: Missing values may be imputed using regression models that predict the missing values based on other available variables.

- Multiple Imputation: Multiple imputation techniques may be employed to create several imputed datasets, which will be analyzed separately and combined to produce overall estimates. In case of Multiple imputation, the method of chained equations (MICE package in R) may be performed if needed.

4. Sensitivity Analysis: Sensitivity analyses will be conducted to assess the impact of the imputation on the results. Different imputation methods will be compared to ensure the robustness of the findings.

5. Documentation: All imputation procedures and decisions will be thoroughly documented to ensure transparency and reproducibility of the analysis.

9. Handling of Missing Data

- Method of Handling Missing Data: See chapter 8.10 above.
- Sensitivity to Missing Data: See chapter 8.10 above.

10. Data Monitoring and Quality Assurance

- Data Monitoring:
 - The study will be monitored according to the monitoring plan to ensure that it is conducted and documented properly according to the protocol, GCP, and all

applicable regulatory requirements. The monitoring function will be organized by the study centres at Reykjavik University and Gothenburg University.

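### Section 8.10 allows single mean, median or regression imputation of staff time and names no primary method, so the error rate of the non-inferiority test is not controlled

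*SAP*

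**What the plan says.** Section 8.10 states that imputation will be used when data are missing. Its scope is general: "The dataset will be examined to identify any missing values in the variables of interest". The mechanism (MCAR, MAR or MNAR) is then to be assessed, and that assessment decides the method. Three options follow, each introduced with a 'may':

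- "Mean/Median Imputation: For continuous variables, missing values may be imputed using the mean or median of the available data"
- regression on other variables in the dataset, with nothing said about adding a random residual or about which predictors must be included
- "Multiple imputation techniques may be employed to create several imputed datasets", with chained equations in R mentioned as a possibility.

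A sensitivity step is promised: "Different imputation methods will be compared to ensure the robustness of the findings". Section 9 only refers back to 8.10.

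For the primary endpoint, section 8.4 says: "The primary analysis will be conducted on the intention-to-treat (ITT) population, including all randomized patients according to their assigned group". Its list of sensitivity analyses contains none for missing staff times. Section 8.8 provides for sensitivity analyses when more than 10% of data are imputed, but only for secondary, tertiary and exploratory endpoints. Section 8.2 keeps descriptive statistics on non-imputed data and has the rate of missing data reported. Section 6 says that "the expected drop-out rate of patients is 20" per cent, and on that basis plans 500 patients per group.

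**The concern.** The primary set is everyone randomised, some loss is expected, and the only rule for missing values is 8.10. Single imputation of the primary endpoint is therefore a permitted route to the headline result.

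Two distinct problems can follow. First, a filled-in mean, median or regression prediction without a random residual carries no variation, yet would enter the mixed model as if it had been measured. The interval is then too narrow. Second, the mean in the first option is not tied to study arm. If one value is used for both arms, the estimated difference shrinks toward zero by the missing share. In a non-inferiority test, a narrow interval or a diluted excess of staff time makes a false claim more likely.

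The rule for choosing does not protect against this. Observed data cannot distinguish MAR from MNAR, so the assessment cannot point to one method. What remains is a choice made after the data are in, on the primary endpoint of an open-label trial.

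**Working it through.** **Inputs.** From section 6: SD 120 minutes, margin 30 minutes, one-sided alpha 1%, power 90%, true difference 0, 500 per group, drop-out 20%. From section 8.4: a 95% confidence interval, that is, one-sided 2.5%. Assumed here: staff time is missing completely at random, equally in both arms, at the 20% given for patient drop-out, with 10% and 30% as a range.

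**The plan's own figure.** n = 2 × (2.326 + 1.282)² × 120² / 30² = 416.5, rounded up to 417 per group. It reproduces.

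**Standard error that the data support.** With 20% missing, 400 per arm are observed: SE = 120 × √(2/400) = 8.49 minutes.

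**Variant A: arm mean, or deterministic regression including group.** The difference is unbiased. The filled-in values lower the apparent variance to 0.8 × 120² while the apparent n stays at 500, so the reported SE = √0.8 × 120 × √(2/500) = 6.79. The ratio is 6.79 / 8.49 = 0.80; in general it is one minus the missing share. At a true excess of exactly 30 minutes, false non-inferiority is:

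- nominal 1%: 1 − Φ(0.80 × 2.326) = 3.1%
- nominal 2.5%: 1 − Φ(0.80 × 1.960) = 5.8%

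**Variant B: one mean pooled over arms.** The expected estimate is 0.8 × 30 = 24 minutes, and the reported SE is about 6.8. False non-inferiority is:

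- nominal 1%: Φ((30 − 24)/6.79 − 2.326) = Φ(−1.44) = 7.5% (7.4% if the small between-arm spread is added to the SE, giving 6.80)
- nominal 2.5%: Φ(0.884 − 1.960) = 14.1%

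**Range of missing share** (Variant B with the between-arm spread included):

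| Missing | A, nominal 1% | A, nominal 2.5% | B, nominal 1% | B, nominal 2.5% |
|---|---|---|---|---|
| 10% | 1.8% | 3.9% | 2.8% | 6.1% |
| 20% | 3.1% | 5.8% | 7.4% | 14.1% |
| 30% | 5.2% | 8.5% | 18.1% | 29.3% |

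**Check with centres.** The formulas ignore centre, so they were checked by simulation: 24 centres of 42 patients, a centre-adjusted estimator, 20% missing, a true excess of 30 minutes, and 8,000 runs for each of three assumed intra-centre correlations (0, 0.3, 0.6; the SAP gives none). At nominal 1%, false non-inferiority was:

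- observed cases only: 0.9–1.0%
- arm mean: 2.8–3.3%
- regression on group and centre: 3.1–3.2%
- pooled mean: 7.6%, 8.9% and 13.9% as the correlation rises

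**The case against.** The best defence is that 8.10 permits single imputation without prescribing it. Multiple imputation is on the same list, and a comparison of methods is promised. That stands: a reader might infer that the plan will bias the trial toward non-inferiority, and the text does not say so. But a comparison of methods does not say which result decides the claim when they disagree, so the gap remains.

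Three further inferences go beyond the text:

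- **That 20% of staff times will be missing.** Section 6 gives 20% as patient drop-out. Section 8.4 counts only the randomised procedure (V1a to V1c), so loss during the second pathway or the PAP phase need not remove the outcome. Staff record the minutes activity by activity (Appendix A), so someone who stops early may have a partial total. The 20% is a planning assumption, which is why a range is shown.
- **That the mean is pooled and the regression deterministic.** Section 8.10 is silent on both. Arm-specific means and a random draw are not excluded. Strong predictors would also reduce the understatement of the SE in regression imputation.
- **That both harms act together and always favour SR.** They belong to different variants. Under MCAR, arm means do not bias the difference. The pooled mean's reported SE matches the spread of its shrunken estimate. Shrinkage helps the claim only if SR truly takes longer. At a true difference of zero there is none. At the midpoints of the section 6 ranges (PSG 470, HSAT 67.5, SR 190) with 40% PSG, the minimum targeted in section 7, standard care averages 0.4 × 470 + 0.6 × 67.5 = 228.5 minutes. SR would then be 38.5 minutes faster, and shrinkage would work against it.

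The last point limits the expected harm but does not remove it. Type I error is judged at the margin, where SR does take 30 minutes longer.

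**Conclusion.** The point holds as a defect in what section 8.10 allows for the primary endpoint. It requires imputation, admits methods that do not keep the nominal error rate, and fixes no primary method. Its size is conditional on single imputation being chosen and on the assumptions listed with the inputs. At 20% missing, nominal 1% becomes 3.1% with arm means or about 7.5% with a pooled mean. Over 10% to 30% missing it becomes 1.8% to 5.2%, or 2.8% to 18.1%. The documents do not show that this harm will occur, so this should be fixed before the primary analysis is run but is not fatal to the design.

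**What to change.** For staff time, remove mean, median and single regression imputation from 8.10, together with the step that picks a method from the assessed mechanism. State that the primary analysis is the section 8.4 mixed model fitted to observed staff times, without imputation. Name multiple imputation by chained equations, run separately by arm with centre in the imputation model, as the sensitivity analysis. A delta-adjusted run, adding minutes to imputed SR times until non-inferiority is lost, would be a useful optional addition because it addresses MNAR directly.

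The cost is SAP wording only; the R package for chained equations is already mentioned. The price is a wider but correct interval: under the assumptions above, an SE of 8.49 rather than about 6.8 minutes.

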All innovation in medicine needs to be justified in terms of cost-benefit. We decided to use stafftime as the primary outcome of the current study. It is estimated that the time of the SR procedure is equal to the time presently used in the SC procedures. Use of the self-applied polysomnography together with machine-learning algorithms of sleep analysis and the digital platform of patient symptom self-reporting will reduce staff time on one hand. On the other hand, user instructions to the patient for the different technologies as well as the evaluation of new information may consume more time compared with the current procedure. We decided to use a non-inferiority study design with 30 minutes as a threshold for equality of staff time within the setting of 24 sleep centers in Europe.

Calculation of the power sample is based on a previous publication (Fischer 2008) and the following assumptions determined from a Delphi round (expert consensus) amongst the participating study centers. More detailed information on staff time for PSG and HSAT currently used at 24 different study sites are not available in the literature. One pilot study for the SR pathway has been performed but no detailed measurement of staff time was performed. However, realistic estimates can be made (see table below).

Work modules	Standard PSG	Standard HSAT	Sleep Revolution	Value
Preparation technical pre/post	15	10	35	
Instructions/Hook up	20-40	5-20	5-30	
Performance of the sleep test	120-480	0 (patient)	0 (patient)	
Evaluation of the sleep test	30-120	5-30	30-90	
Questionnaires	5	5	10	
Additional equipment	0	0	15	
Doctor: interpretation, communication	30-60	15-30	45-60	
Staff time: Estimated range of the mean	220-720	40-95	140-240	
Staff time: Estimated standard deviation of the mean	180	30	60	120

Power calculation:

Significance level (alpha)	1%		
Power (1-beta)	90%	You could say:	
Standard deviation of outcome	120	between the standard and experimental treatment, then 834	
Non-inferiority limit, d	30	sure that the lower limit of a one- sided 99% confidence interval (or equivalently a 98% two-sided	
Sample size required per group	417	confidence interval) will be above the non-inferiority limit of -30.	
Total sample size required	834		
Technical note		Reference	
Calculation based on the formula:		Julious SA. Sample sizes for clinical trials with Normal data. Statis Med. 2004; 23:1921-1986.	

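### The missing-data check in SAP section 8.10 compares imputation methods specified with no departure from missing at random, so it does not test informative loss of staff-time data

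*SAP*

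**What the plan says.** Step 2 of SAP section 8.10 says of the missing-data mechanism: "Missing Completely at Random, Missing at Random, or Missing Not at Random) will be assessed", so that a method can be chosen. Step 3 lists mean or median imputation, regression imputation and multiple imputation (chained equations if needed), each as an option. Step 4 promises sensitivity analyses on the impact of imputation and gives their content in one sentence: "Different imputation methods will be compared to ensure the robustness of the findings". Section 9 refers back to 8.10 for sensitivity to missing data and adds nothing.

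The outcome at stake is staff time. Section 6 describes a "non-inferiority study design with 30 minutes as a threshold for equality of staff time", and section 8.4 analyses all randomised patients in their assigned group. On attrition, section 6 says that "the expected drop-out rate of patients is 20" per cent, taken from the pilot study.

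Four other parts of the SAP touch on the subject:
- Section 8.4 adds a per-protocol analysis, transformation or non-parametric methods, and subgroups.
- Section 8.8 covers sensitivity analyses for secondary, tertiary and exploratory endpoints.
- Section 8.6 has an exploratory analysis of what predicts data loss, in the SR pathway.
- Section 8.2 reports descriptive statistics on non-imputed data and the rate of missing data.

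**The concern.** As described, the methods in step 3 fill gaps from observed data. Mean or median imputation needs data missing completely at random. Regression and multiple imputation, as written, need data missing at random given the variables in the model. Multiple imputation can carry an offset for informative missingness, but none is specified. The observed data cannot separate missing at random from missing not at random, so the assessment in step 2 cannot close the gap.

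The comparison in step 4 is therefore informative about the choice of method and silent on the assumption that the methods share. If staff times are missing for reasons tied to their length, the methods can agree and all be wrong by the same amount.

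This matters for a non-inferiority claim. If the missing SR times were longer than those imputed, the estimated difference would be too small, and the planned check would not show it. The SAP makes informative loss in SR worth examining: section 5 says that success of the self-applied test depends on patient involvement, and the Appendix A time sheet has a line for trouble-shooting during the home studies.

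**Working it through.** **Inputs.** From section 6: SD 120 min, margin 30 min, one-sided alpha 1%, power 90%, 500 per group, 20% drop-out. The assumed true difference is zero ("It is estimated that the time of the SR procedure is equal to the time presently used in the SC procedures"). Section 6 sizes the trial on the "lower limit of a one- sided 99% confidence interval (or equivalently a 98% two-sided" interval, while section 8.4 reports 95% intervals, so both are shown. The difference is taken as SR minus standard care (SC); longer time is worse, so the upper limit is compared with +30.

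**The plan's own figure.** n per group = (2.326 + 1.282)² × 2 × 120² / 30² = 13.02 × 32 ≈ 417, total 834. This reproduces the SAP.

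**Tipping shift.** Let p be the missing fraction in each arm, D the observed difference and δ the excess of the true over the imputed mean among missing SR patients, with SC unshifted.
- SE = 120 × √(2 / (500 × (1 − p)))
- Upper limit = D + z × SE, with z = 2.326 (98%) or 1.96 (95%)
- The shift moves the estimate by p × δ, so the tipping δ = (30 − upper limit) / p

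For p = 0.2 and D = 0: SE = 120 × √(2/400) = 8.49. The upper limits are 19.74 and 16.63. The tipping shifts are (30 − 19.74)/0.2 = 51.3 and (30 − 16.63)/0.2 = 66.8 min.

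| Missing per arm | Observed difference | SE | Upper limit, 98% / 95% | Tipping shift, 98% / 95% |
|---|---|---|---|---|
| 20% | 0 | 8.49 | 19.74 / 16.63 | 51.3 / 66.8 |
| 20% | 10 | 8.49 | 29.74 / 26.63 | 1.3 / 16.8 |
| 10% | 0 | 8.00 | 18.61 / 15.68 | 113.9 / 143.2 |
| 10% | 10 | 8.00 | 28.61 / 25.68 | 13.9 / 43.2 |

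If SC values are shifted as well, the estimate moves by p × (δ in SR − δ in SC), so equal shifts cancel.

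**Can the methods agree and be wrong?** In 400 simulated trials (500 per arm, 20% missing, missing SR patients 60 min longer, one covariate) the full-data difference averaged 11.8 min; arithmetic gives 0.2 × 60 = 12. Arm-mean, overall-mean, regression and multiple imputation gave −0.2, −0.2, −0.3 and −0.3 min. They agreed and missed the same bias. The observed difference was near zero there, where arm-mean and overall-mean imputation are bound to agree.

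**Can they disagree for an irrelevant reason?** Take D = 15 and p = 0.2. Complete cases give 15 + 19.7 = 34.7 (fails). Overall-mean imputation shrinks the difference to 0.8 × 15 = 12 and the SE to 120 × √0.8 × √(2/500) = 6.8, so the limit is 12 + 15.8 = 27.8 (passes). With 95% intervals the limits are 31.6 and 25.3. The verdicts conflict, yet only shrinkage and a falsely small SE have been detected.

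**The case against.** Several stronger readings are tempting, and the SAP does not support them.

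- **That the check must always pass.** It need not: the D = 15 example shows listed approaches giving opposite verdicts. What stands is narrower: neither agreement nor disagreement tests informative missingness.
- **That the SAP commits to missing at random.** It does not. Step 2 lets the mechanism steer the method, multiple imputation is not restricted, and the opening promise of step 4 is open-ended. Even so, the only check that it spells out is the comparison.
- **That 20% of staff times will be missing.** The figure is patient drop-out from a pilot in which, section 6 says, staff time was not measured in detail. The outcome covers V1a to V1c and is recorded by staff, so later losses need not remove it. The 20% is a worst case, and at 10% the tipping shifts roughly double.
- **That the bias favours SR.** Trouble-shooting time has its own line on the sheet, and patients who stop early may skip scoring and consultation and so use less time. SC times may also be lost informatively; standard PSG has the largest assumed SD (180).
- **That 51 min is small because the SAP's SR SD is 60.** This mixes SDs, since the SE rests on 120. Against 120 the shift is 51.3/120 = 0.43 SD, and it is about half the 100-minute width of the SAP's 140–240 range for the SR mean. At zero observed difference, a reader could call that fairly robust.

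It could also be said that the per-protocol analysis covers the point. It uses patients who completed the pathway, so it leaves out those in question. The drop-out analysis in 8.6 does not re-estimate the staff-time difference, and 8.8 does not cover the primary endpoint.

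**Conclusion.** The point holds in limited form. Section 8.10 admits informative missingness, specifies no analysis that departs from missing at random, and offers a comparison of methods as its robustness check. That comparison cannot show how far the non-inferiority conclusion depends on the unseen staff times.

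The dependence ranges from slight to severe: at zero observed difference it takes 114 to 143 min with 10% missing and 51 to 67 min with 20% missing, but at an observed difference of 10 min with 20% missing, 1 to 17 min is enough. These figures assume SD 120, 500 per group, equal missingness per arm, no predictive covariates, no allowance for centre and an SE unchanged by the shift. They do not show that such a shift exists or which arm it would affect. This is an inexpensive improvement to the plan; it is not evidence that the primary result will be wrong.

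**What to change.** For the primary staff-time analysis, amend section 8.10 as follows:

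1. Name multiple imputation by arm, accounting for centre, as the method for missing staff time.
2. Prespecify a delta-adjusted tipping-point analysis that varies the shift added to imputed values in each arm, including SR worsened with SC unshifted. A grid of 0, 15, 30, 45, 60 and 90 min would serve as an example.
3. Report the smallest shift at which the upper limit exceeds 30 minutes, and discuss its plausibility given the observed amount of and reasons for missing time sheets.
4. Do not cite agreement among single and multiple imputation methods as evidence of robustness.

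The cost is a few lines of SAP text and a short loop in the imputation code. The downside is slightly more analysis work and a robustness statement that may turn out less favourable.
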